9.5.2.1 Description of Procedures/Assessments Schedule

The schedules of assessments are presented in [Table 6](#) and [Table 7](#), and details regarding the assessments to be performed are presented in [Section 9.5.1](#).

9.5.3 Appropriateness of Measurements

Planned assessments are standard measurements for this type of study and are considered appropriate. Per the US FDA guidance, demographic data, complete subject medical histories, including cancer treatment history, and baseline disease status are to be for all subjects prior to administration of the first dose of study drug ([FDA Guidance for Industry 2001](#); [European Medicines Agency 2011](#)). Study drug administration data, including dose interruptions and modifications and the associated reason(s), also are to be documented ([FDA Guidance for Industry 2001](#); [European Medicines Agency 2011](#)).

AEs and SAEs will be monitored in this study in accordance with ICH GCP guidelines to ensure the safety of subjects. Furthermore, additional safety assessments conducted during this study, including physical examinations, ECGs, vital signs assessments, and clinical laboratory tests, are widely used and generally recognized as reliable, accurate, and relevant. These tests and procedures also will be monitored in accordance with ICH GCP guidelines.

Tumor response and progression will be assessed using standard criteria for the assessment of disease response in solid tumors.

The effects of H3B-6527 in FGF19 and other FGFR4-related biomarkers and any correlation with safety and antitumor activity will be evaluated during the study.

9.5.4 Reporting of Serious Adverse Events, Pregnancy, and Events Associated with Special Situations

9.5.4.1 Reporting of Serious Adverse Events

All SAEs, regardless of their relationship to study treatment, must be reported on a completed SAE form by email or fax as soon as possible but no later than 24 hours from when the investigator becomes aware of the event.

SAEs, regardless of causality assessment, must be collected through the OTV (ie, 30 days after the last study drug dose). All SAEs must be followed to resolution or, if resolution is unlikely, to stabilization. Any SAE judged by the investigator to be related to the study treatment or any protocol-required procedure should be reported to the Sponsor regardless of the length of time that has passed since study completion.

For urgent safety issues, please ensure all appropriate medical care is administered to the subject and contact the appropriate study team member listed in the Investigator Study File.

It is very important that the SAE report form be filled out as completely as possible at the time of the initial report. This includes the investigator's assessment of causality.

Any follow-up information received on SAEs should be forwarded within 1 business day of its receipt. If the follow-up information changes the investigator's assessment of causality, this should also be noted on the follow-up SAE form.

Preliminary SAE reports should be followed as soon as possible by detailed descriptions including copies of hospital case reports, autopsy reports, and other documents requested by the Sponsor.

The investigator must notify his/her IRB/IEC of the occurrence of the SAE, in writing, if required by their institution. A copy of this communication must be forwarded to the Sponsor or designee to be filed in the Sponsor's Trial Master File.

9.5.4.2 Reporting of Pregnancy and Exposure to Study Drug Through Breastfeeding

Any pregnancy in which the estimated date of conception is either before the last visit or within 30 days of last study treatment or any exposure to study drug through breastfeeding during study treatment or within 28 days of last study treatment must be reported.

If an adverse outcome of a pregnancy is suspected to be related to study drug exposure, this should be reported regardless of the length of time that has passed since the exposure to study treatment.

A congenital anomaly, death during perinatal period, an induced abortion, or a spontaneous abortion is considered to be an SAE and should be reported in the same time frame and in the same format as all other SAEs (see [Section 9.5.4.1](#)).

Pregnancies or exposure to study drug through breastfeeding must be reported by fax or email as soon as possible but no later than 1 business day from the date the investigator becomes aware of the pregnancy. The contact information for the reporting of pregnancies and exposure to study drug through breastfeeding is provided in the Investigator Study File. The Pregnancy Report Form must be used for reporting. All pregnancies must be followed to outcome. The outcome of the pregnancy must be reported as soon as possible but no later than 1 business day from the date the investigator becomes aware of the outcome.

Study drug must be discontinued immediately for any subject who becomes pregnant during the study.

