16. A clinically significant electrocardiogram (ECG) abnormality, including a marked baseline prolonged QTc interval (eg, a repeated demonstration of a QTc interval >450 ms).
17. Significant cardiovascular impairment: history of congestive heart failure greater than New York Heart Association Class II, uncontrolled arterial hypertension, unstable angina, myocardial infarction, or stroke within 6 months of the first dose of study drug; or cardiac arrhythmia requiring medical treatment (including oral anticoagulation).
18. Any other major illness, medical condition or concomitant medication that, in the investigator's judgment, will substantially increase the risk associated with the subject's participation in this study or would compromise the subject's ability to safely complete the study.
19. Males who have not had a successful vasectomy (confirmed azoospermia) or they and their female partners do not meet the criteria above (ie, not of childbearing potential or practicing highly effective contraception throughout the study period or for 90 days after study drug

discontinuation). No sperm donation is allowed during the study period or for 90 days after study drug discontinuation.

20. Hypersensitivity to the study drug or to any of the excipients.
21. Intolerance or hypersensitivity to both CT and MRI contrast material that would preclude the ability to acquire the triphasic liver imaging required by the protocol.
22. An inorganic phosphorus > ULN for the institution. Note: Subjects may be on treatment for hyperphosphatemia, but the levels must be normal at screening to participate in this study. Subjects with high levels on screening may subsequently be treated and rescreened and, should they have stable levels for 2 weeks prior to study, may enter the study.
23. A total or ionized serum calcium > ULN for the institution. Note: Subjects may be on treatment for hypercalcemia, but the levels must be normal at screening to participate in this study. Subjects with high levels on screening may subsequently be treated and rescreened and, should they have stable levels for 2 weeks prior to study, may enter the study.
24. Endocrine changes that may result in increases in calcium or phosphate, including but not limited to hyperparathyroidism and tumoral calcinosis.
25. Past medical history and/or current evidence of tumoral calcinosis or tissue calcification.

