9.1.2.4 Follow-Up Phase

After the Off-treatment Visit (OTV), all subjects who discontinue study treatment, regardless of their reasons for doing so, will be followed for survival via telephone (for those subjects who experience PD or initiate a new anticancer therapy) or office visit (for those subjects still undergoing tumor assessments). Subjects will be followed for survival approximately every 12 weeks for up to 12 months or until 6 cycles after last patient in, death, loss to follow-up, or withdrawal of consent, whichever occurs first. Subjects who discontinue study drug and

have not experienced PD will continue to undergo tumor assessments every 6 weeks until documented PD or another anticancer therapy is initiated.

The data cutoff for the primary analysis will occur once the last subject completes 6 cycles of investigational therapy. Subjects will be allowed to continue treatment until progression or the end of therapeutic benefit from the study drug as determined by Sponsor discussion with investigator.

The end of the study is defined as when the last ongoing subject completes their off treatment visit. The off treatment visit should occur 30 days after final dose with a window of ± 3 days.

The maximum estimated period for each subject on treatment is anticipated to be approximately 4 months. However, subjects may continue to receive study treatment, as long as they demonstrate clinical benefit as judged by the investigator after discussion with the Sponsor or until the end of the study.

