14. Females of childbearing potential should avoid becoming pregnant and use highly effective contraception while on treatment and for at least 1 month after finishing treatment. Females of childbearing potential must not have had unprotected sexual intercourse within 30 days before study entry and must agree to use a highly effective method of contraception (eg, sexual abstinence, an intrauterine device, a contraceptive implant, an oral contraceptive, or have a vasectomized partner with confirmed azoospermia) throughout the entire study period and for 30 days after study drug discontinuation. Sexual abstinence is considered a highly effective method only if defined as refraining from heterosexual intercourse during the entire period of risk associated with the study treatment. The reliability of sexual abstinence needs to be evaluated in relation to the duration of the clinical study and the preferred and usual lifestyle of the subject. Periodic abstinence (calendar, symptothermal, and post-ovulation methods), withdrawal (coitus interruptus), spermicides only, and lactational amenorrhea method are not acceptable methods of contraception. Female condom and male condom should not be used together. Females who are using hormonal contraceptives must have been on a stable dose of the same hormonal contraceptive product for at least 4 weeks before dosing and must continue to use the same contraceptive during the study and for 30 days after study drug discontinuation. Women using oral hormonal contraceptives should add a barrier method.

15. Be willing and able to comply with all aspects of the protocol.

16. Provide written informed consent prior to any study-specific Screening procedures.

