11. Treatment with proton pump inhibitors that cannot be discontinued 3 days prior to the start of study drug and during the course of the study; antacids are permitted except for calcium carbonate antacids (eg, Tums[®]).
12. Use of other investigational drugs within 28 days or at least 5 half-lives (whichever is shorter) before study drug administration.
13. Previous treatment with a selective FGF19-FGFR4 targeted therapy.

14. Use of any live vaccines against infectious diseases (eg, influenza, varicella) within 4 weeks (28 days) of initiation of study therapy.
15. Presence of gastric or esophageal varices requiring active treatment.
16. A clinically significant electrocardiogram (ECG) abnormality, including a marked baseline prolonged QTc interval (eg, a repeated demonstration of a QTc interval >450 ms).
17. Significant cardiovascular impairment: history of congestive heart failure greater than New York Heart Association Class II, uncontrolled arterial hypertension, unstable angina, myocardial infarction, or stroke within 6 months of the first dose of study drug; or cardiac arrhythmia requiring medical treatment (including oral anticoagulation).
18. Any other major illness, medical condition, or concomitant medication that, in the Investigator's judgment, will substantially increase the risk associated with the subject's participation in this study or would compromise the subject's ability to safely complete the study.
19. Males who have not had a successful vasectomy (confirmed azoospermia) or they and their female partners do not meet the criteria above (ie, not of childbearing potential or practicing highly effective contraception throughout the study period or for 90 days after study drug discontinuation). No sperm donation is allowed during the study period or for 90 days after study drug discontinuation
20. Hypersensitivity to the study drug or to any of the excipients.
21. Intolerance or hypersensitivity to both CT and MRI contrast material that would preclude the ability to acquire the triphasic liver imaging required by the protocol.
22. Inorganic phosphorus > ULN for the institution. Note: Subjects may be on treatment for hyperphosphatemia, but the levels must be normal at screening to participate in this study. Subjects with high levels on screening may subsequently be treated and rescreened and, should they have stable levels for 2 weeks prior to study, may enter the study.

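### The protocol sets a 90-day post-treatment precaution for male subjects, but pregnancy reporting can end at day 30 and does not name partners, leaving up to 60 of the 90 days uncovered

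*Protocol*

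**What the plan says.** **Precaution period, men.** Exclusion criterion 19 (Protocol 9.3.2, repeated in the Synopsis) excludes men unless they have had a successful vasectomy, their partner cannot conceive, or the couple is "practicing highly effective contraception throughout the study period or for 90 days after study drug" discontinuation. It adds "No sperm donation is allowed during the study period or for 90 days after study drug" discontinuation.

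**Precaution period, women.** Inclusion criterion 14 (Protocol 9.3.1) requires highly effective contraception "throughout the entire study period and for 30 days after study drug discontinuation".

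**Reporting rule.** Protocol 9.5.4.2 makes reportable "Any pregnancy in which the estimated date of conception is either before the last visit or within 30 days of last study treatment". These are two alternative triggers, and meeting either one is enough. Reported pregnancies are to be followed to outcome. For adverse outcomes thought to be drug-related there is no time limit: "this should be reported regardless of the length of time that has passed since the exposure to study treatment". The section neither defines the last visit nor mentions partners.

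**Visits after treatment.** Protocol 9.1.2.4 states: "The off treatment visit should occur 30 days after final dose", with a window of ± 3 days. Survival follow-up is then by telephone for subjects with progression or a new anticancer therapy, or by "office visit (for those subjects still undergoing tumor assessments"). Tumor assessments in that second group continue every 6 weeks. Survival contacts are about every 12 weeks and appear as Visit 99 in Tables 6 and 7.

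**The concern.** The reporting window appears to have been set for female subjects: its 30 days equal the female contraception period. For men the protocol extends its own precaution to 90 days, and nothing in 9.5.4.2 extends reporting to match. A partner pregnancy conceived late in the 90 days can therefore fall in a period the protocol thought worth a precaution, with no duty to report it or follow it.

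The stake is safety information. Section 7.1.1.2 describes this as the first clinical investigation of the drug, Section 7.1.1.3 says its clinical safety profile is unknown, and safety and tolerability is a primary objective. Section 7.1 notes that liver cancer is more common in men, so male subjects may well be the larger group. A birth defect in the child of an exposed subject is a serious adverse event under 9.5.1.4.2, wording that includes the children of men. Yet routine collection of serious adverse events stops 30 days after the last dose, well before any such birth. The pregnancy report is what starts follow-up to birth, so a pregnancy outside the window may have no outcome recorded.

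**Working it through.** The documents give no figure on this point to reproduce. The check is interval arithmetic.

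**Inputs**
- Male precaution period after study drug: 90 days (criterion 19).
- Fixed reporting trigger: conception within 30 days of last treatment (9.5.4.2).
- Alternative trigger: conception before the last visit (9.5.4.2; day not defined).
- Off-treatment visit: day 27 to 33 (9.1.2.4).
- Tumor assessments off treatment without progression: every 42 days from the last one (9.5.1.2.1).
- Survival contacts: about every 84 days, taken here as counted from the off-treatment visit.

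Days are counted from the last dose, which is assumed to be the discontinuation date.

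**Formula**

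Uncovered days = 90 − max(30, day of last visit), with a minimum of 0. Share = uncovered days / 90.

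| What counts as the last visit | Day | Uncovered days | Share of 90 |
|---|---|---|---|
| Off-treatment visit | 27 or 30 | 90 − 30 = 60 | 66.7% |
| Off-treatment visit, end of window | 33 | 90 − 33 = 57 | 63.3% |
| Tumor-assessment office visit | 42 | 90 − 42 = 48 | 53.3% |
| Tumor-assessment office visit | 63 | 90 − 63 = 27 | 30.0% |
| Tumor-assessment office visit | 84 | 90 − 84 = 6 | 6.7% |
| Any visit at day 90 or later | ≥ 90 | 0 | 0% |
| First survival contact, if it counts as a visit | 111 to 117 (27 to 33, plus 84) | 0 | 0% |

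The office-visit days are examples. Days 42 and 84 arise if the last scan fell on the day of the last dose; day 63 arises if it fell 21 days earlier.

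**Can a survival contact be relied on to close the gap?** After progression the contact is a telephone call, and the protocol does not say whether a call is a visit. Nor is the contact guaranteed. Survival follow-up can end 6 cycles after the last patient in, which is 6 × 21 = 126 days. For the last subject enrolled, treated for T days, the first contact falls at about T + 30 + 84 = T + 114 days after his start. This is within 126 days only if T ≤ 126 − 114 = 12. Section 9.1.2.4 anticipates treatment of up to about 4 months, so men enrolled late may never have that contact.

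**The contraception clauses side by side.** The female clause joins its two periods with *and*; the male clause joins them with *or*. Read literally, either male period alone would satisfy criterion 19. The sperm-donation sentence also uses *or*, but within a prohibition, where *or* bars both periods.

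**The case against.** There is a fair case that this is smaller than it looks.

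- **The rule has two triggers.** A reader might infer that reporting always stops at 30 days, and that two-thirds of the period is uncovered for every man. The documents do not support that. The trigger tied to the last visit extends the window for anyone with a later visit, and the gap runs from 0 to 60 days. This stands, and 60 days is a maximum.
- **There are provisions without a time limit.** A reader might infer that nothing conceived after day 30 need ever be reported. That is also wrong: 9.5.4.2 keeps adverse outcomes suspected to be drug-related reportable indefinitely, and 9.5.4.1 does the same for related serious adverse events. This stands, but only in part. Both depend on someone suspecting a link, and neither requires the pregnancy itself to be reported and followed, so normal or unattributed outcomes may be missed.
- **The rule speaks of any pregnancy.** This wording can include partners, and the same section refers separately to a subject who becomes pregnant. Partner handling may also be set out in the Pregnancy Report Form, the Investigator Study File or the consent form, none of which was available for review. The documents therefore do not show that partners are excluded, only that the protocol leaves their inclusion implicit.
- **A contraception period and a reporting window have different purposes.** The protocol never calls the 90 days a risk window, so the difference is not a strict contradiction. This is correct. The point is that the reporting window matches the precaution for one sex and not for the other, without explanation.
- **Materiality is low.** No endpoint, dose-limiting toxicity rule or SAP analysis is affected, and few events are to be expected.

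**Conclusion.** The point holds as a gap of up to 60 of 90 days. For a man who stops for progression and is then followed only by telephone, with the off-treatment visit as his last visit, 57 to 60 days (63% to 67%) fall outside mandatory reporting and follow-up to outcome. For men with later visits the gap is smaller and may be zero. The size rests on three assumptions: the undefined last visit is the off-treatment visit, telephone contacts do not count as visits, and the last dose and discontinuation fall on the same date. It concerns only men not exempted by vasectomy or by a partner who cannot conceive.

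On criterion 19, only the contraception clause needs attention. A reader might also take the *or* in the sperm-donation sentence as permitting donation in one of the two periods; as a prohibition it does not.

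This is a modest safety-reporting improvement, worth making because it is cheap and because, in a first-in-human study, an unrecorded exposure outcome is hard to recover later.

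**What to change.** 1. Reconcile 9.5.4.2 with criterion 19 (Synopsis and 9.3.2) so that the reporting window covers the precaution periods the protocol itself states for each sex. This point takes no position on how long those periods should be.
2. Define the last visit in 9.5.4.2, and say whether a telephone survival contact counts.
3. State that pregnancies in female partners of male subjects are reportable and followed to outcome, subject to the partner's consent.
4. Reconcile the contraception clause of criterion 19 with the parallel wording of inclusion criterion 14, so that it is clear whether both periods apply. Leave the sperm-donation sentence as it is.

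The cost is a few sentences of protocol text, partner consent text where it does not already exist, and a few additional reports. The SAP needs no change.

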9.5.4.3 Reporting of Events Associated with Special Situations

9.5.4.3.1 **REPORTING OF ADVERSE EVENTS ASSOCIATED WITH STUDY DRUG OVERDOSE, MISUSE, ABUSE, OR MEDICATION ERROR**

AEs associated with study drug overdose, misuse, abuse, and medication error refer to AEs associated with uses of the study drug outside of that specified by the protocol. Overdose, misuse, abuse, and medication error are defined as follows:

Overdose	Accidental or intentional use of the study drug in an amount higher than the protocol-defined dose.
Misuse	Intentional and inappropriate use of study drug not in accordance with the protocol.
Abuse	Sporadic or persistent intentional excessive use of study drug accompanied by harmful physical or psychological effects.
Medication error	Any unintentional event that causes or leads to inappropriate study drug use or subject harm while the study drug is in the control of site personnel or the subject.

All AEs associated with overdose, misuse, abuse, or medication error should be captured on the Adverse Event CRF and reported using the procedures detailed in [Section 9.5.4.1](#) even if the AEs do not meet serious criteria. Abuse is always to be captured as an AE. If the AE associated with an overdose, misuse, abuse, or medication error does not meet serious criteria, it must still be reported using the SAE form and in an expedited manner but should be noted as nonserious on the SAE form and the Adverse Event CRF

9.5.4.4 Expedited Reporting

The Sponsor must inform investigators and regulatory authorities of reportable events, in compliance with applicable regulatory requirements, on an expedited basis (ie, within specific time frames). For this reason, it is imperative that sites provide complete SAE information in the manner described above.

